### 3.19 Data Analysis

Analytical processes used to address the research questions and the quantitative data are presented below.

### **3.19.1 Analysis of Quantitative Data**

Graduate Package 23.0 of the Statistical Package for Social Sciences (SPSS) provided tools to analyze the data required to achieve the research objectives:

In the pretest of dependent variables, data from the mothers and infants were evaluated for homogeneity, normality, variability, and data normality in the pretest. Nevertheless, the variance test for the nurses' data was not homogeneous since we were dealing with the same group, the data were normally distributed and the variances between the groups were equal, and the sample size was acceptable (no less than 30 cases per group). The number and proportion were stated as continuous variables and categorical variables. Continuous variables were compared for normally distributed variables ('mothers' and 'infants') using the independent t-test and variance analysis (ANOVA/ANCOVA). Pearson's chi-square test was used because the independent variables were nominal categorical variables. The Chi-square test was applied with normally distributed data to establish associations between independent variables, such as age, years of service as RN, years of working in NICU and educational qualification level, and dependent variables: perception, knowledge and outcomes improvement: weight gain, length of hospitalization stay and breastfeeding rates. In addition, the Shapiro-Wilk test was used to test data normality for both the pre and post-test, as the sample was below 50 per arm. To assess the effect of the structured kangaroo care educational program (KC-EP) on mothers', infants' and nurses' outcomes, for the data on mothers, infants and nurses, the general linear model (GLM) univariate analysis of variance and covariance analysis was used. GLM and repeated measures were used to analyze the main effects and interaction effects of KC outcome variables, and to examine the hypotheses of the outcomes.

Table 3.4: Summary of Statistical Analysis of Quantitative Data Plan

No.	Objectives	Measurement Variables	Statistical analysis
1.	Are there any statistically significant differences in mothers' perception, knowledge, perceived barriers regarding KC, and stress related to 'premature infants admission to NICU' after participation in the KC-EP?	Perception, knowledge, perceived barriers and stress related to premature infants' admission to NICU mean scores Effect of KC-EP KC performance (Ordinal data)	Descriptive - mean, SD, skewness and kurtosis Chi-square test, GLM, repeated measure (RM) & Pearson Eta Squared.
2.	Does kangaroo care improve weight gain patterns in premature infants between control and experimental groups at $T_0$ , $T_1$ , and $T_2$ ?	Weight gain patterns (grams) mean score KC compliance Duration (hours/weeks) Frequency and Percentage (Continuous data)	Descriptive – mean, SD, skewness and kurtosis Chi-square test, GLM and t-test.
3.	Does kangaroo care decrease the length of hospitalization stay for premature infants between control and experimental groups?	Length of hospitalization stay Frequency and percentage (Continuous data)	Descriptive – mean, SD, skewness and kurtosis Chi-square test, GLM and test
4.	Does kangaroo care improve breastfeeding rates for premature infants between control and experimental groups?	Breastfeeding rates KC compliance Frequency and percentage (Continuous data)	Descriptive – mean, SD, skewness and kurtosis Chi-square test, GLM and t-test.
5.	Are there any statistically significant differences in nurses' perception, knowledge, and practice regarding KC before and after participation in the KC-EP?	Perception, knowledge, practice mean scores Effect of KC-EP (Ordinal data)	Descriptive - mean, SD, skewness and kurtosis Independent t-test GLM, RM & Pearson Eta Squared.

The key influence of an explanatory variable is its direct effect on the outcome variables (Field, 2011). Additionally, the effects of covariate and covariate interaction with KC can be included in GLM univariate analysis. This covariance analysis is an extension of the variance analysis to include a covariate/confounder component (Field, 2011). This covariance is linearly related to the dependent variable, and its inclusion in the analysis will minimize the error associated with the covariance analysis (Field, 2011). The test is appropriate since

categorical variables are both independent and dependent variables. Therefore, covariance analysis was used to correct the observed effects on the outcome variables of potential confounders. The summary of the statistical analysis used for all research questions is outlined in Table 3.14. Each of the statistical tests is two-tailed. A p-value below 0.05 was assumed to show statistical significance.

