### **2.3.7 Patterns of Weight Gain**

Patterns of weight gain are closely monitored for all infants in the NICU setting. Preterm infants with slow growth tend to be slower in development according to research studies. Weight gain in the premature infant depends on the gestation and prematurity of the infant. A few days after birth, the infant will start losing some weight but then regain it after a while. According to Davidson, Ladewig & London, (2012) KC helps to increase growth parameters among premature infants. Thus, if the infant is born very soon and is also very tiny, its weight gain might be as little as about 5 gm a day, whereas the gain in weight could be as high as 20 gm a day for bigger infants as well as those delivered closer to their due date. Discharge policies also include a specific bodyweight criterion prior to discharge, regardless of where the premature infant has been treated in the hospital or medical care service. Most hospitals

have a predetermined weight protocol, which premature infants should meet before they can be allowed to return home. Some hospitals evaluate the routine pattern of the premature infant's weight gain. If it corresponds to their criteria of a healthy weight gain, the infant may be allowed to be discharged. In this study setting, weight gain is monitored three times a week. Discharge criteria are a baseline body weight of between 1.7kg to 1.8kg, a good sucking reflex, being clinically stable and the mother having the confidence to take care of her premature infant (after attending a briefing session on the care of the premature infant: personal hygiene, feeding and Cardio Pulmonary Resuscitation (CPR) in the NICU by the doctor in charge).

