***b) Section B: Infant's Kangaroo Care Progress Record (KCPR) or Data Sheet***

Section B assessed the progress of the premature infant in terms of primary and secondary outcomes. The primary outcome variables were weight gain and LOS, while the secondary outcomes were breastfeeding rate or feeding status. All nine (9) items were adapted from the original article by Singh, Amritanshu and Mukherjee, (2014) and Biswas, Malpani & Ekka, (2016) with a slight modification and format to satisfy the research goals relevant to the main and secondary monitoring requirements of the use of KC to assess outcomes. The variables consisted of baseline temperature, age of KC initiation (week/days), weight at KC initiation (g/days), weight gain velocity (g/days), duration of KC (in hour/day), duration of stay (days), types of milk (EBM or breastfeeding), initiation of breastfeeding (weeks) and weaning from breastfeeding (weeks) for both groups. The KCPR booklet was designed and presented to the

respective control and experimental groups. The difference in the KCPR booklet was the knowledge needed for the experimental group to get the input given to the control group for preterm infants (routine activities and standard care) and KC performance. The data for the preterm infants in the control group were documented according to standard practice care or routine practice in the NICU. [Please refer to Appendix F(a) and F(b)].

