### **3.16.4 Method of Data Collection for Infants**

The researcher recruited the control group of premature infants first and then the experimental group after the nursing intervention program had been completed. The preterm infants in both groups were recruited based on infant admission days and according to mother-infant dyad condition. Firstly, all preterm infants between 28 and 36 + 6 days of gestation (n=48) were recruited by the researchers to participate in the study. The first

recruitment was assigned to the control group. The second recruitment of preterm infants who conformed to the inclusion criteria, i.e. clinically stable and ready to perform KC, was assigned to the experimental group (n=48) after written consent was given by their mothers. Those whose mothers refused to participate were excluded from the study. In the experimental group, data from the preterm infants were collected from the recruitment day until they reached 3 months old. A total of 48 newborn preterm infants from the same setting were given routine care (under servo-controlled radiant warmer or in a cradle with room heaters or blankets) and matched by corrected age. Feeding mode at admission to either group was monitored and jotted down, according to the route of feeding: tube feed, spoon-feed or breastfeeding. Before allocation to a group, it was ensured that the preterm infant was tolerating enteral feeds (over 24 hours) and had no regurgitation at age 28 to 36+6 day weeks of gestation. Corrected age was calculated using the Premature Baby Corrected Age Formula and classified between 28 to 36+6 days weeks of gestation. The baseline weight was calculated from the birth weight and weight on recruitment at T0, and outcome weight gain calculated from the weight on discharge, T1, and T2; this was recorded in the KCPR booklet provided. The body weight of the preterm infant was documented, after removing its clothes, using an electronic weighing scale with an accuracy of 5g at least 2 hours after the last feed and twice a week on Tuesdays and Saturdays according to the hospital protocol for weighing babies. Body weight was measured using a T- scale machine and recorded in grams (g).

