After the preterm infants were allocated to the control group or experimental group, they were observed daily, and all observations related to the outcomes of the study were documented in the KCPR booklet i.e. velocity of weight, temperature before, during and after, mode of feeding, type of milk taken and duration of KC provided (in hours/day/week), date of admission and date of discharge in days. In the study by Biswas, Malpani & Ekka, (2016) temperature measurement was taken 10 minutes after KC. However, in this study the

temperature measurement was taken 10 minutes before, 20 to 30 minutes during KC and 10 minutes after the implementation of KC and a regular clinical examination was given in a minimal period of time to avoid hypothermia and cold stress. In the experimental group, duration of KC (in an hour/day) was measured from an accumulated daily 1 hour per day, 4 to 5 hours a week. However, according to Ludington-Hoe, Susan, Morgan, K. & Abouelfetoh (2008), KC is best provided 1 hour a day and 7 days a week until discharge. KC was continued until the premature infant was 3 months old, according to the study requirements. If any problems were detected during KC, they were either rectified or the preterm infant was disqualified from the study. Premature infants were discharged when they showed a good sucking reflex with breast or bottle feeding and had been gaining weight of more than 15g/day to 20g/day for at least three successive days and had achieved a predetermined weight of 1.7kg, in accordance with hospital protocol. On discharge, the nurses routinely advised mothers to come for follow-up until their infant had reached a weight of 2500 grams and to continue breastfeeding. For primary and secondary outcomes, the data from both groups were collected at T0, T1, and T2. The premature infants were followed-up until they were discharged. Conversations and communication between mothers and researchers continued through telephone calls or Whatsapp chat groups accordingly. All related information on KC was shared through the WhatsApp chat group among mothers in the experimental group so that they would remain KC compliant and continue KC at home.

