#### a) Infant Outcome Variables Data

In Phase I and Phase III, the outcome data were collected from the control group and experimental group of infants. The outcome data were recorded continuously from the day of recruitment at the corrected age of between 28 to 36/6 weeks of gestation in the NICU until the infants reached 3 months old after discharge. At any stage, if a premature infant in the experimental group did not meet the requirements for research (e.g. deteriorated during KC

or needed phototherapy treatment for jaundice), the infant was excluded from the study. During the two phases, similar outcome variables and confounding variables were obtained. The outcome variables reflected the outcomes of the premature infants. Specifically:

i) KC implementation duration in hours (in hours; 24 hours = 1 day); The duration of KC in the intensive care unit measures the number of hours the infant was attached to or bonded with their mother. According to the posttest it was measured in hours and days per week. According to the World Health Organization (2003), each KC session should ideally last at least 1 hour, in order to get the physiological effects and for brain development and maturation. In this study, the researcher decided to practice accumulative 1 hour per day and accumulative 4 to 5 hours per week (KC duration).

ii) Weight gain of the infant in daily weight (in a day; 1 day = 24 hours)

The weight gain of the premature infant represents the amount the infant's weight increased or decreased in a day. 1 day equal to 24 hours.

iii) The decrease in hospitalization stay or Length of hospitalization stay (LOS) in the NICU (in a day; 1 day = 24 hours);

The length of stay at the NICU measures the number of days the preterm infant was admitted to the intensive care unit and was treated in a day, 1 day equivalent to 24 hours. iv) Confounding variables

All standard demographic and clinical measures assessed by preterm infants with critical care were collected, including:

- demographic data: gestation, age, gender, ethnicity and weight gain for infants;
- type of milk (breastfeeding or formula milk)
- duration of feeding status i.e. week started and week discontinued breastfeeding and mode of feeding, bottle, or spoon-feeding.

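### For weight gain and length of stay, the plan does not say whether the unadjusted t-test or ANCOVA decides H2, and its infant confounder list omits baseline weight while including an outcome

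*Combined protocol and SAP*

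**What the plan says.** Section 3.9(b) fixes the outcome hierarchy for infants: "The primary outcome variables were weight gain and LOS, while the secondary outcomes were breastfeeding rate or feeding status". Section 3.3 states that assignment is not random. Sections 3.7.2 and 3.16 describe two consecutive recruitment periods, control from February to July 2018 and experimental from later in 2018 to April 2019.

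On the analysis, section 3.19.1 says: "Continuous variables were compared for normally distributed variables ('mothers' and 'infants') using the independent t-test and variance analysis (ANOVA/ANCOVA". Table 3.4 gives chi-square, GLM and t-test for weight gain (row 2). For LOS (row 3) it gives chi-square, GLM and a test whose type is not printed. The sample size in 3.7.2 is derived for a two-sample t-test.

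The plan also provides for adjustment. Section 3.19.1 assigns assessment of the programme's effect on infant outcomes to GLM variance and covariance analysis. It adds that "the effects of covariate and covariate interaction with KC can be included in GLM univariate analysis", and closes by saying that covariance analysis corrects for potential confounders. The confounders are listed in 3.16.4(a)(iv). The first item reads "demographic data: gestation, age, gender, ethnicity and weight gain for infants"; the others are type of milk and the duration and mode of feeding.

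Baseline size and maturity are recorded. Section 3.9(a) collects birth weight, gestational age at birth and corrected age on recruitment. Section 3.16.4 states "The baseline weight was calculated from the birth weight and weight on recruitment at" T0, and says that infants were "and matched by corrected age", without giving a matching rule.

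**The concern.** In consecutive, non-randomised cohorts nothing in the design equalises starting weight, and only the matching statement bears on maturity. If either differs systematically between the two periods, an unadjusted t-test attributes the consequence to the education programme, in whichever direction the difference runs. Because the plan ranks neither method, either an unadjusted or an adjusted p-value below 0.05 could be reported as the answer to H2.

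The adjusted route is not safe as written either. Following the confounder list would leave out baseline weight. It would also put weight gain among the covariates of a weight-gain model, and would condition on feeding duration, which is observed after the intervention starts and may be affected by it.

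**Working it through.** **Planning basis.** The plan's n reproduces: 2 × (1.96 + 0.842)² × 0.8² / 0.54² = 34.5, rounded up to 35 per group (34.65 with the plan's rounding), and 35 / 0.7 = 50 after the 30% allowance. This is an unadjusted two-sample calculation. The text names a difference of 8.41 but the formula uses 0.54, so I do not express any bias in weight gain as a share of a planned effect.

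**LOS and starting weight.** Section 3.16.4 allows discharge when the infant has been gaining 15–20 g/day and "had achieved a predetermined weight of 1.7kg, in accordance with hospital protocol". For infants below that weight:
- 50 g: 50/20 = 2.5 days to 50/15 = 3.3 days
- 100 g: 100/20 = 5.0 days to 100/15 = 6.7 days

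**LOS and gestation.** Section 1.2 cites stays of 36 down to 11 days over 32 to 36 weeks. If linear, this is (36 − 11)/4 = 6.25 days per week.

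**Comparator.** The cited kangaroo-care effect on LOS (section 2.4.3 on LOS) is 17.68 − 11.46 = 6.22 days. One week of gestation, or roughly 100 g below the discharge weight, is therefore about as large as the whole cited effect.

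**Weight gain.** Section 2.3.7 says gain depends on gestation, from about 5 g/day in very early, tiny infants, "whereas the gain in weight could be as high as 20 gm a day for bigger infants" and those born nearer term. It ties neither figure to a week, so it supports the dependence but not a slope.

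**Error rate of an unadjusted t-test for LOS with no true effect.** With 48 per group the rejection rate comes from the noncentral t on 94 df, with noncentrality (shift in days / LOS SD) × √24. The documents give neither the imbalance nor the spread of recruitment weight, so both are assumptions. The LOS SD must be compatible with them: if weight has an SD of 300–500 g and each 15–20 g is worth a day, weight alone implies a LOS SD of 300/20 = 15 to 500/15 = 33 days.
- At that implied SD, a 50 g imbalance gives 7.7% (500 g) to 12.8% (300 g); 100 g gives 16.3% to 36.6%.
- Adding independent variation of 6.83 days to the implied SD gives 7.5–11.9% and 15.5–33.4%.
- A narrower spread raises the rates. The cited study of newborns under 1.5 kg has a pooled LOS SD of √((4.32² + 8.64²)/2) = 6.83 days. At that SD, 50 g gives 43–66%, but the weight SD could then be at most 6.83 × 15 = 102 g to 6.83 × 20 = 137 g.

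**Does adjustment work?** Write d for the imbalance in covariate SDs and ρ for the covariate–outcome correlation, both assumed. For d = 0.2 and ρ = 0.5–0.9, the unadjusted test rejects in 7.7–14.1% of trials; for d = 0.5, in 22.8–58.8%. In simulations of the same cases (4,000 runs each; linear relation, covariate measured without error), ANCOVA rejects in 4.9–5.7%.

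**The case against.** The strongest reply is that the plan already adjusts. Section 3.19.1 gives the assessment of the programme's effect and the testing of hypotheses to GLM, says covariance analysis corrects for confounders, and 3.16.4 lists gestation and age. This stands: a reader might infer from the t-test entries that no adjustment is planned, and the documents do not support that. What remains is that the t-test is also listed for the same outcomes, no text says which result decides, no covariate is fixed for either model, and the list is faulty.

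Three stronger inferences also fail.
- **Near-certain false positives.** A reader might combine the 6.83-day LOS SD with a 300–500 g weight spread and conclude that 50 g gives 43–66% and 100 g gives 94–99.7% false positives. Those inputs contradict each other, because that weight spread by itself implies a LOS SD of 15–33 days.
- **Chance imbalance.** With a weight SD of 300–500 g, the standard error of the group difference is 61–102 g, so imbalances of this size look likely even without selection. But chance imbalance is already in the t-test's standard error; a simulation with random imbalance rejected in 5.1% of trials. Only a systematic difference biases the test.
- **Ignored matching.** Matching on corrected age, if it was carried out, would limit age imbalance. Ignoring positive within-pair correlation makes intervals too wide, which is conservative. Baseline weight is therefore the stronger half of the point.

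**Conclusion.** The concern holds in a limited form. Adjustment is present but under-specified and partly wrong: the deciding analysis is not named, baseline weight is missing from the confounder list, and an outcome and a post-baseline variable are in it.

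The documents' own figures show that starting size and maturity matter for both outcomes, and that for LOS a modest systematic difference could match the cited effect. They do not show that such a difference exists, nor its size. The 8–13% for a 50 g imbalance rests on an assumed weight SD of 300–500 g and on the gram-to-day conversion, which applies only to infants below the discharge weight. The 6.25 days per week assumes linearity in a cited outside population.

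**What to change.** In section 3.19.1 and Table 3.4 rows 2–3, name one GLM/ANCOVA as the deciding analysis for each outcome, and report the adjusted group difference with its 95% CI.
- **Weight gain:** group, recruitment weight and corrected age at recruitment.
- **LOS:** group, birth weight and gestational age at birth. LOS is counted from NICU admission (1.7.11), while recruitment may follow stabilisation (3.13, 3.16.2). Values taken at recruitment can therefore already reflect hospital days that belong to the outcome.
- Keep the t-test as descriptive, drop chi-square as a between-group test for these rows, and complete the test name in row 3.
- In 3.16.4(a)(iv), add birth weight and recruitment weight. Exclude weight gain and feeding duration from the covariates of these two models.

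The cost is wording plus two degrees of freedom per model (94 to 92 residual with 96 infants); every covariate is already collected. Adjustment does not remove calendar-time differences between the cohorts, which remain a limitation to report.

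Separately, the discharge weight appears as 1.7 kg (2.3, 3.16.4), 1.7–1.8 kg (2.3.7) and 1.8 kg (3.4, Appendix P). These passages must be reconciled, because LOS depends on the threshold.

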## **1.8 Organisation of thesis**

The thesis is organized in six chapters to facilitate clarification and understanding of the study.

Chapter One presents an introduction to the research, and contains background, statement of problems, study significance, research questions, objectives, hypothesis, and operational definitions.

Chapter Two contains an appraisal of the literature on subjects, practice, recommendations, and previous studies on KC among premature infants related to weight gain, LOS, breastfeeding rates and KC-EP and conceptual framework.

Chapter Three includes a description of the methodology, research design, research tools, sampling procedures, and methods of collecting data. This section also describes the specifications of the pilot test, data analysis strategies, and ethical considerations.

Chapter Four describes the major results from the quantitative design. This includes the results of the effectiveness of the KC-EP for mothers', premature infants' and nursing outcomes; comparison of mothers' perception, knowledge, perceived barriers and level of stress between control and experimental groups at T0, T1 and T2; comparison of premature infant weight gain, LOS and breastfeeding rates between control and experimental groups at T0, T1 and T2; comparison of nurses' perception, knowledge and practice at pretest-posttest. Results for the mothers', premature infants' and nursing outcomes are presented. It also presents the association between the demographic characteristics of the participants and the main outcomes of the study.

Chapter Five presents a discussion of the results of this study. Quantitative findings are incorporated into the discussion of the specific issues arising from the findings. The findings of the current study can be used to complement and reach conclusions in relation to previous research.

Chapter Six provides the conclusion of the study, followed by the consequences and guidelines for nursing, education and clinical practices. Each section addresses the limitations and strengths of the study. The chapter ends with an overview of the findings of the study.

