##### ***Section A: Demographic Characteristics***

Section A collected the demographic characteristics of mothers in the NICU at UMMC. All fourteen (14) variables were designed to gather the baseline data and follow the study's objectives. The variables included in this study were maternal age (years), race, religion, marital status, delivery type: spontaneous vertex delivery (SVD) or caesarean section, parity of mother: primipara or multipara, highest educational level, occupational status, employment sector status, maternity leave status, household income (RM), breastfeeding status, post-partum stress status (pre and post) and KC training course. The rationale for using these data was to assess if the variables chosen had any effect on the perception, knowledge, perceived barriers, and level of stress of the participants.

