***a) Section A: Infant's Demographic Characteristics***

Section A collected the premature infants' demographic characteristics data from both groups. All nine (9) variables were formatted to gain information on the baseline data of the infants. The variables included gender, race, birth weight (kg), gestational age at birth (weeks), corrected age on recruitment (weeks), corrected age on discharge (weeks), mode of feeding (tube feed, syringe-feed, cup-feed or breastfeed), type of milk, expressed breast milk (EBM) or breastfeeding, initiation of breastfeeding (weeks) and weaning from breastfeeding (week/month). The rationale for using these variables was to assess if the selected variables had an impact in terms of primary and secondary outcomes on the perception, awareness, perceived barriers and stress of the mothers.

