##### ***a) Section A: Demographic Characteristics***

Section A data were collected based on the demographic characteristics of the nurses in UMMC's NICU. All eight (8) variables were formatted to gather the baseline data and fulfill the study objectives. The variables included in this study were: age, race, marital status, working experience (RN), working experience in NICU, neonatal nursing certification, KC practice in NICU, and KC training experience. The rationale for measuring such data was to determine whether the selected variables had an effect on the perception, knowledge, and practices of the study participants in relation to KC.

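### Characteristic-by-outcome association tests, uncounted in the plan, are each judged at p<0.05 with no exploratory label and no control for their number

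*Combined protocol and SAP*

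**What the plan says.** Section 3.19.1 (Analysis of Quantitative Data) says: "The Chi-square test was applied with normally distributed data to establish associations between independent variables, such as age, years of service as RN". The list continues with years working in the NICU and educational level. These are set against "dependent variables: perception, knowledge and outcomes improvement: weight gain, length of hospitalization stay and breastfeeding rates". The same section gives one decision rule for all tests: "Each of the statistical tests is two-tailed" and "A p-value below 0.05 was assumed to show statistical significance".

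Section 1.8, describing the results chapter, says: "It also presents the association between the demographic characteristics of the participants and the main outcomes of the study".

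The instrument sections explain why the characteristics are collected:

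- Mothers (3.8.1, Section A), 14 variables: "to assess if the variables chosen had any effect on the perception, knowledge, perceived barriers, and level of stress of the participants".
- Nurses (3.10.1, Section A), 8 variables: "to determine whether the selected variables had an effect on the perception, knowledge, and practices of the study participants in relation to KC".
- Infants (3.9, Section A), stated as 9 variables: "to assess if the selected variables had an impact in terms of primary and secondary outcomes on the perception, awareness, perceived barriers and stress"; the outcomes named here are maternal ones.

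The associations are not among the specific objectives (1.5.2), the hypotheses (1.6) or the research questions in Table 3.4. No section calls them exploratory, ranks them or adjusts for their number.

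**The concern.** The wording is confirmatory: associations are to be established, and the characteristics are said to have an effect. With one 0.05 threshold for each of an open-ended set of tests, some associations can be expected to pass by chance. They would be reported in the same chapter as the group comparisons, with nothing in the plan to tell a reader that they carry less weight.

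A second problem lies in the same sentence. Read literally, it pairs years as a registered nurse and years in the NICU with infant weight gain, length of stay and breastfeeding. Nurses work rotating shifts (3.15.5), the infant record forms in Appendix F hold no nurse identifier, and nurse questionnaires carry only the nurse's own code (3.17, 3.18). No documented link joins a nurse to an infant, so those pairs have no common unit of analysis.

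**Working it through.** The plan states neither a number of association tests nor a family-wise error rate, so there is no figure of its own to reproduce. The count has to be derived.

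**Inputs**

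- Per-test level 0.05, two-tailed (3.19.1).
- Predictors named in 3.19.1: age, years as RN, years in NICU, education = 4.
- Outcomes named in 3.19.1: perception, knowledge, weight gain, length of stay, breastfeeding = 5.
- Mothers: 14 variables, 4 outcomes (3.8.1).
- Nurses: 8 variables, 3 outcomes (3.10.1).

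**Number of tests, m**

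- Named pairs only: 4 × 5 = 20.
- Without the nurse-only predictors against infant outcomes (2 × 3 = 6): 20 − 6 = 14.
- Every maternal and nurse variable against the outcomes named for it: 14 × 4 + 8 × 3 = 56 + 24 = 80.

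**Expected false positives if no association is real:** 0.05 × m. This needs no independence assumption.

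**Chance of at least one:** 1 − 0.95^m if the tests are independent. For correlated tests it is the probability that any of m equally correlated normal statistics exceeds 1.96 in absolute value, found by integrating over a common factor. The correlations 0.5 and 0.8 are assumptions chosen to show a range; the documents give none.

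| m | Expected false positives | Independent | Correlation 0.5 | Correlation 0.8 |
|---|---|---|---|---|
| 14 | 0.7 | 51% | 35% | 20% |
| 20 | 1.0 | 64% | 42% | 22% |
| 80 | 4.0 | 98% | 73% | 34% |

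Real associations lower the expected number. If a quarter of the 80 were real (an assumption), it would be 0.75 × 4.0 = 3.0. Every entry in the last three columns is well above 5%.

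The variable counts are themselves inconsistent. Section 3.10.1 gives eight nurse characteristics and 3.20.3 gives nine; section 3.9 states nine infant variables and lists ten. The number of tests therefore cannot be fixed from the text.

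**The case against.** The strongest reply is that only 3.19.1 specifies association tests. Sections 3.8.1, 3.9 and 3.10.1 explain why baseline data are collected and name no test. The outcome list in 3.19.1 also omits perceived barriers, stress and practice, which supply 14 × 2 + 8 × 1 = 36 of the 80. This stands: 80 is an inference, and the range has to start at 14 or 20. It does not remove the point, because the predictor list is open and even the low end leaves a sizeable chance of a false claim.

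A reader might go further in four ways that the documents do not support.

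- **116 tests.** Adding 9 infant variables × 4 maternal outcomes gives 80 + 36 = 116; using the 3 infant outcomes instead gives 107. This again rests on a data-collection rationale. Several infant items (corrected age at discharge, milk type, breastfeeding initiation, weaning) are themselves discharge or feeding measures, so crossing them with length of stay or breastfeeding is partly circular and a null calculation does not fit.
- **Repetition at T0, T1 and T2.** No section says that associations are tested at each time point. Length of stay has one value per infant, and nurses are measured twice.
- **False claims almost certain.** That follows only for the wide count with little correlation. Section 1.8 promises to present the associations; it does not call them established.
- **Nurse-by-infant tests definitely planned.** Section 3.10.1 ties nurse variables only to nurse outcomes, and age and education are maternal variables too. The sentence may simply compress several populations. It still needs splitting.

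It is also fair to say that these tests are already secondary, being outside the objectives and hypotheses, and that some of the characteristics serve as potential confounders in the covariance analysis. The first limits the seriousness; the second limits the remedy.

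**Conclusion.** The concern holds as a matter of labelling and error control for secondary associations. As written, the rule yields about 0.7 to 4 expected false positives if no association is real. The chance of at least one is about 51% to 98% under independence, falling to about 20% to 34% at a correlation of 0.8.

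These figures assume that each pair is tested once and that each test holds its 5% level, which sparse chi-square tables may not do exactly. The lower count rests on the pairs named in 3.19.1, and the upper count on the collection rationales in 3.8.1 and 3.10.1.

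The nurse-to-infant point holds only as a drafting fault: the literal sentence pairs variables that no instrument links. A reader might infer that the main result is in doubt; it is not, because these tests lie outside the group comparisons under the three hypotheses.

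**What to change.** In 3.19.1:

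1. Change the stated purpose from *to establish* to *to explore* associations.
2. State that all tests of participant characteristics against outcomes are exploratory and are reported as effect sizes with 95% confidence intervals, with no significance claim. If claims are wanted, apply Benjamini-Hochberg at a 5% false discovery rate within each of the mother, infant and nurse families, listing the pairs in each family beforehand.
3. Split the sentence by population, so that nurse characteristics are paired only with nurse outcomes.
4. State that neither the exploratory label nor any false discovery rate result is used to choose confounders for the covariance analysis. In a non-randomised comparison, such screening could drop real confounders.

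The cost is a few sentences and, if claims are kept, one adjustment step. No new data or design change is needed. The downside is that fewer associations can be called significant.
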